12.10. Concomitant Medication

Concomitant medication use will be tabulated.

12.11. Disposition

Subject disposition will be tabulated and will show the number of subjects enrolled, and the number of subjects completing the study. All reasons for discontinuation will be listed and summarized.

12.12. Analysis Plan for Primary Objectives/Aims

In the efficacy evaluable population, our primary analysis will be to estimate RPS at 1 year with a 95% confidence interval. Kaplan-Meier curve will also be estimated for the relapse free survival curve.

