	 Patients with diagnosis of immunodeficiency or those receiving chronic systemic corticosteroid therapy or other immunosuppressive therapy (except inhaled steroids) within 28 days of the first dose of study drug History of psychiatric illness/social situations that would limit compliance with study requirements. Clinically significant infections as judged by the treating investigator. Clinically significant is defined as an active infection requiring IV antibiotics 				
	- Known HIV infection or chronic hepatitis B or C.				
STATISTICAL	Null Hypothesis: 1 year RFS with postoperative adjuvant durvalumab				
CONSIDERATIONS	therapy in patients with persistent esophageal cancer following neoadjuvant				
	chemoradiotherapy and esophagectomy is 50% or less.				
	Alternative Hypothesis : 1 year RFS with postoperative adjuvant				
	durvalumab therapy in patients with persistent esophageal cancer following				
	neoadjuvant chemoradiotherapy and esophagectomy is 75% or greater.				
	Acceptable Type I (alpha) error: 5%				
	Acceptable Type II (beta) error: 20%				
	Power : 80%				
	Phase II, open label, single arm, single-stage study.				
TOTAL	Total n=39, 34 efficacy evaluable and allowing for up to 5 unevaluable.				
NUMBER OF	Subjects who receive less than 6 months of durvalumab for reasons				
SUBJECTS	unrelated to disease progression or toxicity will be replaced.				
ESTIMATED					
ENROLLMENT	Estimated 18 months				
PERIOD					
ESTIMATED					
STUDY	Estimated 20 months				
DURATION					

INDEX

SECTION PAGE

IE	MA	8
	BACKGROUND & RATIONALE	9
	OBJECTIVES, ENDPOINTS AND OUTCOME MEASURES	15
	Objectives	15
	Endpoints	16
	Outcome Measures	16
	ELIGIBILITY CRITERIA	17
	Inclusion Criteria	17
	Exclusion Criteria	18
	SUBJECT REGISTRATION	19
	TREATMENT PLAN	20
	Pre-medication	20
	Drug Administration	20
	Supportive Care:	20
	Concurrent Therapy	20
	Restrictions during the study	21
	DOSE MODIFICATIONS	22
	Dose Modifications	22
	STUDY CALENDAR & EVALUATIONS	
	Screening	
	On Treatment	
	Protocol therapy discontinuation	54
	Safety Follow-up: 30 days (±7 days) after last dose of protocol therapy	54
	At Recurrence:	55
	Follow-up	55
	CRITERIA FOR DISEASE EVALUATION	55
	BIOLOGICAL CORRELATIVES	57
	DRUG INFORMATION	59
	Drug Names:	
	Drug Class:	
	Formulation, Packaging and Storage	
	Availability and Distribution	
	Preparation	60
	Administration	
	Precautions	
	Side Effects	
	ADVERSE EVENTS	
	Definitions	61
	Reporting	65
	IND Safety Reports Unrelated to This Trial	68

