Historical outcomes of patients who receive chemoradiotherapy followed by surgical resection and are noted to have persistent disease at the time of surgery are poor with 50% of them recurring in the first year (34). We expect durvalumab to improve the relapse free survival at 1 year rate by 25%. The null hypothesis is that 1 year RFS with postoperative adjuvant durvalumab therapy in patients with persistent esophageal cancer following neoadjuvant chemoradiotherapy and esophagectomy is 50% or less. Alternative hypothesis is that 1 year RFS with postoperative adjuvant durvalumab therapy in patients with persistent esophageal cancer following neoadjuvant chemoradiotherapy and esophagectomy is 75% or greater. With a maximum acceptable type I error (the probability of concluding that the drug is effective when it is actually not effective) of 0.05, and acceptable type II error (the probability of concluding that the drug is not effective when it is actually effective) of 0.20, the calculated sample size is 23 evaluable patients. If the total number of patients free of relapse at 1 year is less than or equal to 15, the drug would not be considered for further study. Up to 26 will be enrolled to allow for 10% unevaluable for efficacy. Subjects who receive less than 6 months of durvalumab for reasons unrelated to disease progression or toxicity will be replaced. Estimated accrual period is 18 months; follow up period of 12 months. To improve accuracy for estimating the primary endpoint (1 year RFS) with a 95% confidence interval, an additional 11-16 patients beyond the initial planned 23 evaluable will be enrolled for a target of 39 enrolled and at least 34 patients evaluable for 1 year RFS (to allow for approximately 10% unevaluable). With n=34 evaluable, if the 1 year RFS is 75%, a 95% two-sided confidence interval will have a half-width of 15% (using normal-approximation).

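### Section 12.12 plans only a 95% interval and no rule against the 50% null at 34–39 evaluable; the one stated cutoff belongs to the one-sided 5% test at n=23

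*Combined protocol and SAP*

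**What the plan says.** The primary objective (synopsis and section 2.1.1) is comparative: whether adjuvant durvalumab improves 1-year RFS over historical rates.

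Section 12.6 takes the historical outcome as "poor with 50% of them recurring in the first year" and sets a directional pair of hypotheses, 50% or less against 75% or greater. It continues: "With a maximum acceptable type I error (the probability of concluding that the drug is effective when it is actually not effective) of 0.05". The limit on the type II error is 0.20. The result is 23 evaluable patients, with no further study of the drug if 15 or fewer are free of relapse at 1 year. The synopsis repeats the 5% and 20% error rates and the cutoff of 15. Neither place says whether the 5% is one-sided or two-sided.

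Section 12.6 then adds 11–16 patients, for 39 enrolled and at least 34 evaluable. The stated reason is a more accurate 95% interval. That interval is described as two-sided, with a half-width of 15% at n=34 by normal approximation. No cutoff is given for the larger sample.

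Section 12.12 is the analysis plan for the primary objective: "our primary analysis will be to estimate RPS at 1 year with a 95% confidence interval" (RPS is evidently RFS), plus a Kaplan-Meier curve. It does not mention a test, an interval method, the 50% null or the count rule.

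**The concern.** The design and the analysis plan answer different questions. The design sizes a test of 50% with stated error rates; the analysis plan estimates a rate. That would be harmless if a usable decision rule stood elsewhere, but the only one was derived for 23 patients and was not restated when the sample grew by about half or more.

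At 34–39 evaluable, whoever writes the report must therefore choose how to judge the result against 50%, possibly after seeing the data. Two choices lie to hand. One is the printed count of 15, which is far too lenient at the new size. The other is to ask whether the two-sided 95% interval excludes 50%, which is nominally a 2.5% one-sided criterion and depends on an interval method that 12.12 does not name. At stake is whether a borderline result, such as 23 of 34, is reported as an improvement.

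**Working it through.** **Inputs.** Null rate 0.50, alternative 0.75, type I error 0.05, type II error 0.20, n=23, fail at 15 or fewer, at least 34 evaluable, 39 enrolled (all section 12.6). X is the number alive and relapse free at 1 year, treated as binomial with every evaluable patient's status known.

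**1. The plan's own sample size.** With success at 16 or more of 23:
- alpha = P(X ≥ 16 | n=23, p=0.50) = 0.0466
- power = P(X ≥ 16 | n=23, p=0.75) = 0.8037

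The smallest n with a one-sided exact alpha of at most 0.05 and power of at least 0.80 is 23, with cutoff 16. The one-sided normal approximation agrees: (1.645×0.5 + 0.842×√(0.75×0.25))² / 0.25² = 22.5, rounded up to 23. A two-sided 5% test would need 30 (exact) or 29 (normal). So the design is a one-sided 5% test, although the documents do not use the word.

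**2. The plan's own half-width.** 1.96×√(0.75×0.25/34) = 0.146, about 15%. This reproduces.

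**3. The printed cutoff at the new size.** If 16 or more still counted as success:
- n=34: P(X ≥ 16 | p=0.50) = 0.696
- n=39: P(X ≥ 16 | p=0.50) = 0.900

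**4. Cutoffs at 34–39.** The test cutoff is the smallest k with P(X ≥ k | p=0.50) ≤ 0.05. The exact-interval (Clopper-Pearson) cutoff is the smallest k whose two-sided 95% lower limit exceeds 0.50. The normal-approximation cutoff is the smallest k with k/n − 1.96×√((k/n)(1−k/n)/n) > 0.50. Power is at p=0.75.

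| n | One-sided 5% test: cutoff, alpha, power | Exact 95% interval: cutoff, power | Normal-approximation 95% interval: cutoff, power |
|---|---|---|---|
| 34 | 23, 0.029, 88.1% | 24, 78.9% | 23, 88.1% |
| 35 | 23, 0.045, 92.4% | 24, 85.8% | 24, 85.8% |
| 36 | 24, 0.033, 90.8% | 25, 83.3% | 24, 90.8% |
| 37 | 24, 0.049, 94.2% | 25, 88.9% | 25, 88.9% |
| 38 | 25, 0.036, 92.9% | 26, 86.8% | 25, 92.9% |
| 39 | 26, 0.027, 91.4% | 27, 84.5% | 26, 91.4% |

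The exact interval needs one more success than the test at every n. The normal approximation needs one more only at n=35 and n=37.

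**5. One borderline result, 23/34 = 67.6%.**
- One-sided exact p = 0.029: rejects 50%.
- Normal-approximation 95% interval: 51.9% to 83.4%, excludes 50%.
- Wilson 95% interval: 50.8% to 80.9%, excludes 50%.
- Exact 95% interval: 49.5% to 82.6%, includes 50%.

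**6. An interval that matches the test.** The one-sided 95% exact lower bound (the lower end of a two-sided 90% exact interval) is 52.2% at 23/34 and 49.2% at 22/34. It gives the same cutoff as the test at every n from 34 to 39.

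**The case against.** The strongest reply is that nothing here is wrong in itself. A one-sided 5% test reported beside a two-sided 95% interval is common in single-arm phase II trials. The extra patients were added for precision, and 12.12 delivers that precision. An interval has no type I error until someone decides by it, and no section says that anyone will. If someone did, a 2.5% criterion would be stricter than the 5% maximum, so type I error would not be breached. All of this stands.

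A reader might infer more from the figures than the documents support:

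- *That the planned analysis falls short of 80% power.* The 78.9% needs a Clopper-Pearson interval used as the decision rule, and no section specifies either. It is 1.1 points short, at n=34 only; at n=35–39 the same rule has 83–89%. The normal approximation, the only method the documents name (for the half-width), gives 88.1% at n=34. The 9-point gap between 88.1% and 78.9% is measured against a power the protocol never claims.
- *That test and interval disagree throughout 34–39.* That is true of the exact interval only.
- *That the sponsor intends 16 successes among 34 or more to count as success.* The rule is printed with the 23-patient calculation. It might be meant for the first 23 evaluable, where its error rates hold, but the documents do not say so, and the added patients would then play no part in the decision.

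What the reply does not answer is that the comparative primary objective has no stated decision rule at the size the trial will reach.

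**Conclusion.** The point holds as a gap in specification. The design is a one-sided exact 5% test at n=23, and the analysis plan for 34–39 evaluable contains no test, no interval method and no cutoff against 50%.

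The larger consequence is the outdated count rule: type I error of 0.70 to 0.90 if 16 or more were carried to n=34 or n=39. The smaller one is a single-count ambiguity if the 95% interval is used to decide. It arises at every n from 34 to 39 with the exact interval, and at n=35 and 37 with the normal approximation.

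The conclusion rests on three assumptions. The 5% is one-sided, which is inferred from the directional hypotheses and the match at n=23. The endpoint is analysed as a simple proportion. Between 34 and 39 patients are evaluable. The documents do not support a claim that the trial is underpowered or that its stated type I error has been breached. The matter should be settled before the data are analysed.

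**What to change.** In section 12.12, state that the conclusion on the primary objective rests on the exact one-sided binomial test of 50% at the 5% level, at the achieved number of evaluable patients. Give the minimum number relapse free: 23, 23, 24, 24, 25 and 26 for n=34, 35, 36, 37, 38 and 39. Alpha is then at most 0.05 and power at 75% is 88–94%.

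Report the matching one-sided 95% exact lower bound, so that the reported limit and the test cannot disagree. Keep the two-sided 95% interval as the precision statement, and name its method.

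Reconcile section 12.6 and the synopsis: say that the 5% is one-sided, and either replace the cutoff of 15 or mark it as belonging to the 23-patient design.

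The cost is two sentences and a short list of cutoffs in 12.12, matching edits in 12.6 and the synopsis, and one more limit in the results table. Sample size, assessments and data collection do not change.

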12.13. Analysis Plan for Secondary Objectives/Aims

In the safety population, toxicity will be summarized by rates and 95% confidence intervals. Toxicity analysis will be carried out after 30 days following receipt of the final dose of the study drug by the last study patient. We will tabulate AEs, AESIs, and imAEs, both with and without considering drug attribution.

12.14. Analysis Plan for Correlative/Exploratory Objectives

In the efficacy evaluable population, change in PD-L1 expression from diagnosis to surgery will be assessed using a paired t-test or Wilcoxon signed-rank test as appropriate.

Changes in PD-L1 expression, Immunoscore values, and changes in CTCs over time will be correlated with 1 year RFS using two-sample tests or Wilcoxon rank sum tests as appropriate. We will also explore time to event analyses with RFS using log-rank tests.

Differential gene expression will be performed in R using DESeq2. These files will be downloaded and uploaded to Partek Genomics Suite v6.6 for visualization. Pathway analysis will be performed using Ingenuity Pathway Analysis. CIBERSORT analysis to identify the immune cell make up based on gene expression will also be performed.

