2.1.3. Correlative/ Exploratory Objectives

- To assess changes in PD-L1 expression with chemoradiotherapy in esophageal cancer.
- To analyze possible predictive biomarkers of 1 year RFS including PD-L1 expression (at diagnosis and in residual disease) in tumor cells and tumor infiltrating lymphocytes (by histology and gene expression analysis by pathway analysis and CIBERSORT), both within the tumor and in surrounding connective tissue.

- To assess the Immunoscore (based on numeration of lymphocyte populations CD3/CD45RO, CD3/CD8, CD8/CD45RO) within the center and invasive margins of the tumor and correlate it with 1 year RFS.
- To analyze the correlation between changes in circulating tumor cell numbers in response to PD-L1 inhibition and 1 year RFS in patients with residual esophageal cancer.

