3. ELIGIBILITY CRITERIA

3.1.Inclusion Criteria

Subject must meet all of the following applicable inclusion criteria to participate in this study:

3.1.1 Written informed consent and HIPAA authorization for release of protected health information obtained from the subject prior to performing any protocol-related procedures, including screening evaluations.
 NOTE: HIPAA authorization may be included in the informed consent or obtained

NOTE: HIPAA authorization may be included in the informed consent or obtained separately.

- **3.1.2** Age \geq 18 years at the time of consent.
- **3.1.3** ECOG Performance Status of 0-1 within 28 days prior to registration for protocol therapy.
- **3.1.4** Females of childbearing potential and males must be willing to use two effective methods of contraception (See section 5.5.1) from the time consent is signed until 3 months after treatment discontinuation.
- **3.1.5** Females of childbearing potential must have a negative serum pregnancy test within 14 days prior to registration for protocol therapy.

NOTE: Female subjects are considered of childbearing potential unless they are surgically sterile (they have undergone a hysterectomy, bilateral tubal ligation, or bilateral oophorectomy) or they are ≥ 60 years old and naturally postmenopausal for at least 12 consecutive months. See section 5.5.1.

- 3.1.6 Histological evidence of persistent residual esophageal adenocarcinoma including gastroesophageal junction adenocarcinoma following definitive concurrent chemoradiotherapy (carboplatin and paclitaxel or cisplatin and 5-FU) in the surgical sample (esophagus or lymph node or both) obtained at the time of esophagectomy.
 NOTE: Persistent residual disease is defined as follows (modified from College of American Pathologists Guidelines):
 - No residual tumor (Grade 0, complete response, 0% tumor). This group will not be included in this study.
 - Marked response (Grade 1, 0-<10% residual tumor)
 - Moderate response (Grade 2, 10-50% residual tumor)
 - No definite response (Grade 3, >50% residual tumor)
- **3.1.7** Minimum of 1 month and maximum of 3 months from surgical resection with no evidence of disease progression at the time of enrollment.
- 3.1.8 Must have adequately recovered from surgery as judged by the treating investigator.
- **3.1.9** Laboratory values must be obtained within 28 days prior to registration for protocol therapy.

- White blood cell count (WBC) \geq 3 K/mm³

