9. BIOLOGICAL CORRELATIVES

9.1 Planned Correlative Studies:

- Assessment of changes in PD-L1 expression with chemoradiotherapy in esophageal cancer and correlate with 1 year RFS.
- Analysis of possible predictive biomarkers of 1 year RFS including PD-L1 expression (at diagnosis and in residual disease) and tumor infiltrating lymphocytes (by histology and gene expression analysis by pathway analysis and CIBERSORT), both within the tumor and in surrounding connective tissue.
- Assessment of the Immunoscore (based on numeration of lymphocyte populations CD3/CD45RO, CD3/CD8, CD8/CD45RO within the center and invasive margins of the tumor and correlate it with 1 year RFS
- Analysis of the correlation between changes in circulating tumor cell numbers in response to PD-L1 inhibition and 1 year RFS in patients with residual esophageal cancer

9.2 Source of Tissue Specimens for Correlative Studies:

Specimens from the time of initial diagnosis (archived tissue) and the specimens obtained at the time of surgery (residual tumor and any positive lymph node) are mandatory (if available) for correlative studies.

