9.3 PD-L1 expression using Tissue Microarrays (31)

FFPE specimens obtained at the time of initial diagnosis as well as at the time of surgical resection.

Automated QIF analysis using the AQUA method utilizing commercially available antibody.

9.4 Generation of Gene Expression Data

9.4.1 Blood:

Whole blood will be collected in standard BD Vacutainer EDTA tubes and frozen at -80C. Refer to the Correlative Laboratory Manual (CLM) for collection, processing, labeling, and shipping instructions.

9.4.2 Tumor Specimens:

Specimens from the time of initial diagnosis (archived tissue) and the specimens obtained at the time of surgery (residual tumor and any positive lymph node) will be submitted by sites to the Big Ten CRC biorepository. Refer to the CLM for collection, processing, labeling, and shipping instructions.

9.4.3 Sequencing Methods:

For each sample, DNA & RNA will be extracted using the Qiagen All Prep Universal DNA/RNA/miRNA kit (Qiagen, Valencia CA). Briefly, 100ng of DNA will undergo a highly multiplexed PCR reaction to amplify all exons of 409 genes known to be mutated in cancer (Sanger Gene Census) using the Ion Ampliseq Comprehensive Cancer Panel. The Ion Ampliseq Comprehensive Cancer Panel is specifically designed for amplification of both formalin-fixed paraffin embedded samples as well fresh/frozen tissue. Subsequent to amplification, libraries will be sequenced on an Ion Proton Sequencer using 200bp fragment chemistry and an Ion

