12.7. Criteria for Stopping the Study

Safety: The first six subjects treated with at least one dose of study drug will be observed for a minimum of 60 days. During the 6th subject's 60-day observation period, further accrual will be halted to evaluate "unacceptable toxicities warranting early closure of the trial" defined as:

- 1) Any definitive durvalumab-related death. A durvalumab-related death will be continuously monitored throughout the trial and the trial will be suspended for re-evaluation whenever such an event is confirmed.
- 2) Any unexpected and previously unreported grade 4 toxicities definitely related to durvalumab.

If such events are observed in one subject, the DSMB will discuss and provide recommendations to the sponsor-investigator. If such events are observed in two or more subjects, the trial will be suspended for re-evaluation.

Pneumonitis of grade 3 and 4 will be continuously monitored. An overall rate of 20% or above would be considered unacceptable. If the probability of the grade 3/4 pneumonitis rate being less than 20% drops below 0.1, the trial will be suspended for re-evaluation.

Population	Definition
Enrolled	This will comprise all patients who meet the eligibility criteria and are registered onto the study.
Efficacy Evaluable	This will comprise all patients who receive at least one dose of trial drug and either undergo at least one post-baseline assessment or die before any evaluation.
Safety	This will comprise all patients that receive at least one dose of durvalumab

12.8. Analysis Datasets

12.9. Subject Characteristics and significant protocol violations

Subject demographics and subject baseline clinical characteristics will be listed and summarized for all subjects enrolled, including age, gender, and race by phase. Counts, means, medians, standard deviation, minimum and maximum values will be presented. Significant protocol violations will be listed.

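### The PD-L1 change from diagnosis to surgery predates durvalumab but is tested only in the efficacy evaluable set, with no rule for which surgical specimen enters the pair

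*Combined protocol and SAP*

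**What the plan says.** The first correlative objective (section 2.1.3) is: "To assess changes in PD-L1 expression with chemoradiotherapy in esophageal cancer". Section 9.3 names the two time points of the assay: "FFPE specimens obtained at the time of initial diagnosis as well as at the time of surgical resection". Section 12.14 sets the population and the test: "In the efficacy evaluable population, change in PD-L1 expression from diagnosis to surgery will be assessed using a paired t-test" or a Wilcoxon signed-rank test.

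The Analysis Datasets table (section 12.8) defines that population: "This will comprise all patients who receive at least one dose of trial drug and either undergo at least one post-baseline assessment", or who die before any evaluation. The same table defines a wider Enrolled set (eligible and registered), which this test does not use.

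Eligibility fixes the timing (section 3.1.7): "Minimum of 1 month and maximum of 3 months from surgical resection with no evidence of disease progression at the time of enrollment".

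On tissue, section 3.1.6 accepts residual disease "in the surgical sample (esophagus or lymph node or both) obtained at the time of esophagectomy". Section 9.2 lists what is submitted for the correlative studies: "the specimens obtained at the time of surgery (residual tumor and any positive lymph node) are mandatory (if available"). Section 12.5 defines the PD-L1 endpoint on the residual tissue from esophagectomy without naming a site. No section says which surgical specimen is paired with the diagnostic one.

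**The concern.** The analysis set should fit the question. Here the question is what chemoradiotherapy did to PD-L1, and both measurements are fixed before the patient enters the trial. Whether the patient later receives durvalumab, or is later assessed, cannot alter either value. Filtering on those events can only discard valid pairs.

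A second gap lies in the pairing itself. A patient whose only residual disease is nodal is eligible, and positive nodes are submitted. If the diagnostic sample came from the primary tumor, such a patient's pair would compare primary with node. Any difference between the two sites would then be read as an effect of chemoradiotherapy. The same gap affects patients with both kinds of surgical tissue, because someone must choose one. The change scores are also correlated with 1 year RFS in section 12.14, so the choice carries forward.

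**Working it through.** 1. **The plan's own figures.** The plan gives no sample size, standard deviation, effect size or power for the paired PD-L1 test. Its evaluable number rests on RFS: section 12.6 quotes a 95% half-width of 15% at n = 34 and 75% RFS. Check: 1.96 × √(0.75 × 0.25 / 34) = 0.146, which agrees after rounding. The synopsis adds 39 enrolled with up to 5 unevaluable (5/39 = 12.8%).

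2. **Timing.** Diagnosis comes first, then chemoradiotherapy, then surgery, then 1 to 3 months, then enrollment and the first dose. Both PD-L1 samples therefore predate durvalumab.

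3. **How many pairs the set removes.** Section 12.6 describes the 34 as evaluable for 1 year RFS, whereas the synopsis calls them efficacy evaluable. The set that governs the test is looser: one dose plus one post-baseline assessment, or death before any evaluation. It excludes only patients who are never dosed, or who are dosed, alive and never assessed. A patient replaced for receiving less than 6 months of durvalumab can still belong to it. Therapy must start within five business days of registration (section 4), and visits are every 4 weeks (section 2.3.2), so exclusions should be few. On the planned numbers the loss is 0 to 5 pairs.

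4. **Ceiling on precision.** At most 39 pairs replace 34, and √(34/39) = 0.934, so the standard error falls by at most 6.6%. For a two-sided 5% paired t-test (noncentral t):
   - the change detectable with 80% power is 0.495 SD with 34 pairs and 0.460 SD with 39;
   - power for an assumed change of 0.5 SD is 80.8% with 34 and 86.1% with 39;
   - if only 60% of patients have both samples (assumption), the counts are about 20 and 23 pairs, and the detectable change is 0.660 and 0.611 SD.

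5. **Netting off node-only patients.** Their share is not given. At an assumed 5% to 20% of 39, they number 2 to 8. Starting from the maximum of 39 pairs, 37 to 31 primary pairs remain. Against 34, the standard error ratio runs from √(34/37) = 0.959 to √(34/31) = 1.047, that is, from 4.1% narrower to 4.7% wider.

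6. **Site mixing, as illustration only.** Let f be the share of pairs that use a node and s the node-to-primary shift in SDs of the paired difference. With no true chemoradiotherapy effect, the mean difference is f × s and its SD is √(1 + f(1 − f)s²). Neither f nor s is in the documents. With 34 pairs, the rejection rate of a nominal two-sided 5% test is:
   - f = 10%: 5.9% (s = 0.5) or 8.4% (s = 1.0);
   - f = 20%: 8.6% or 18.3%;
   - f = 30%: 13.1% or 33.9%.

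**The case against.** A reader might infer that the plan will lose five pairs. The documents do not support that. Five is the planning allowance beside a number sized for 1 year RFS, and the defined analysis set is easier to enter. The recoverable pairs may also not exist: archived tissue is scheduled at Cycle 1 Day 1 and is mandatory only if available, so patients registered but never dosed may have submitted none.

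A reader might also infer that the PD-L1 comparison is biased by site. That is not shown. The protocol speaks only of archived diagnostic tumor tissue and does not say that it is from the primary. Section 9.2 is one submission list serving several assays and does not say that a node enters the PD-L1 pair. Collection and processing are deferred to the Correlative Laboratory Manual, which is not among the documents and might settle specimen choice.

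There is also a case for one common set. Section 9.1 joins the PD-L1 change to its correlation with 1 year RFS, and section 12.1 allows further exploratory analyses and minor changes without amendment.

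These points limit the size and priority of the concern. They do not give dosing or later assessment any bearing on a change that is already complete, and they do not supply a pairing rule. A common set is reasonable for the RFS correlations, which the proposed change leaves alone.

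**Conclusion.** The population point holds. The paired test of a pre-treatment change is restricted by post-enrollment conditions that are irrelevant to it. The loss is 0 to 5 pairs and probably few. The 6.6% reduction in standard error is a ceiling that assumes all 39 patients have evaluable tissue at both times. Provided that every dosed patient also counts as enrolled, the wider set can only keep or add pairs.

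The specimen point holds as a missing rule. Mixed-site pairs are possible as the text stands, but the diagnostic site, the share of node-only patients and any site shift are not given. The size of a bias, or its existence, cannot be derived from the documents, and the rejection rates above illustrate assumed inputs only.

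The objective is exploratory, and the primary and safety conclusions are unaffected. This is a low-priority improvement.

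**What to change.** In section 12.14, change the population for this one test to all enrolled patients with evaluable PD-L1 at both diagnosis and surgery. Keep the efficacy evaluable set for the correlations with RFS.

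State which surgical specimen enters the pair:
- main analysis: same-site, primary-to-primary pairs;
- nodal PD-L1: reported separately;
- sensitivity analysis: all pairs;
- number of pairs: stated for each analysis.

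Settle this before assay results are seen, and check it against the Correlative Laboratory Manual. The specimen site should be recorded with each PD-L1 result, because the descriptive site variable in section 2.3.2 has no explicit node-only category.

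The cost is a few sentences of analysis text, with no added samples or visits. The downside is that node-only patients leave the main paired analysis. This may offset the pairs gained from the wider set, or leave fewer than 34 if such patients are common.
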